7.8 Sample size considerations

- **Sub study 1:** The sample size calculation is based on the primary endpoint described for sub study 1 (time in level 2 hypoglycaemia). A sample size of 24 patients is determined to have at least 80% power to detect a reduction in the percentage of time spent with a glucose value <3.0 mmol/l (level 2 hypoglycaemia), assuming a relative treatment reduction of 50% from a percentage of time spent with glucose value <3.0 mmol/l of 3%, standard error of 2.5%, and type I error rate (2 sided) of 5%. To account for approximately 25% dropouts, the final sample size is set to 30 patients. As there are currently no adequate data on CGM in patients with pancreatogenic diabetes to inform sample size calculations, assumptions are based on findings in older adults with long-standing type 1 diabetes who have an increased risk of hypoglycaemia⁷.
- **Sub study 2:** This is a retrospective cohort study based on data already collected in Diabetesdatabasen and the sample size will therefore be dictated by the number of individuals in the

database. Previous population-based studies from our group have shown that the proportion of patients with PPDM among patients clinically diagnosed type 1 or type 2 diabetes is approximately 1.5%^{4,22}. In Diabetesdatabasen there are currently >5000 unique adult individuals registered, and thus we expect to identify at least 75 PPDM cases which should provide sufficient statistical power to the planned analyses according to a previous study from our group²².

- **Sub study 3:** This is a cross-sectional survey. No previous studies have evaluated the prevalence of self-reported severe hypoglycaemia and related risk factors in patients with PPDM. However, according to recent population-based registry data from our group, patients with PPDM have a risk of hospitalization for hypoglycaemia comparable to that observed for individuals with type 1 diabetes (*unpublished data*). In type 1 diabetes, the yearly prevalence of self-reported severe hypoglycaemia range between 10–53%²³. Thus, we consider a sample size of 200 patients will provide sufficient power to obtain prevalence estimates with reasonable precision and allow for multivariate modelling of putative risk factors associated with severe hypoglycaemia.

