7.1 Study designs

- **Sub study 1** is a prospective open-label crossover randomized controlled study of the effect of CGM on hypoglycaemia compared to SMBG in PPDM patients
- **Sub study 2** is a retrospective cohort study of long-term glucose variability, as determined by visit-to-visit HbA1c levels, in PPDM patients compared to matched individuals with type 2 diabetes
- **Sub study 3** is a multicentre cross-sectional study based on patient-reported outcomes (PROs)

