7.6 Outcomes

7.6.1 Primary endpoints

- **Sub study 1:** Difference (monitoring with CGM vs. SMBG) in time spent with glucose value <3.0 mmol/L (level 2 hypoglycaemia) during the last two weeks of each study period
- **Sub study 2:** Long-term glucose variability (up to 48 months) expressed as difference in visit-to-visit HbA1C VIM (Variability Independent of the Mean) between PPDM patients and individuals with type 2 diabetes patients
- **Sub study 3:** Proportions of patients with severe hypoglycaemia during the preceding 12 months. Hypoglycaemic endpoints are defined according to the latest ADA recommendations²¹

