8.3 Plan for statistical analyses

8.3.1 Statistical methods

- **Sub study 1:** CGM metrics collected in periods with monitoring using CGM vs. SMBG are compared using multiple linear regression models. Further, regression models are fitted to investigate associations between baseline characteristics and measures of glucose variability.
- **Sub study 2:** HbA1c variability metrics are compared between PPDM and type 2 diabetes patients using multiple linear regression models. Hb1Ac level trajectories are visually characterized and latent class analysis is used to define distinct patient clusters.
- **Sub study 3:** Prevalence estimates of hypoglycaemia are reported as point prevalence estimates with 95% confidence intervals. Logistic and Poisson regression models are fitted to investigate associations between patient characteristics and hypoglycaemia risk.

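### Does calling the 2.5% variability input a standard error undermine the sample size of 24 in sub study 1?

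*Protocol*

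**What the plan says.** Section 7.8 of the protocol states for sub study 1: "A sample size of 24 patients is determined to have at least 80% power". The effect is given by "assuming a relative treatment reduction of 50% from a percentage of time spent with glucose value <3.0 mmol/l of 3" percent, so the target difference is 1.5 percentage points. The remaining inputs are "standard error of 2.5%, and type I error rate (2 sided) of 5" percent. Section 7.8 gives no other measure of spread, no within-patient correlation and no named test. It says that the assumptions come from a trial in older adults with long-standing type 1 diabetes, because adequate data in pancreatogenic diabetes were lacking.

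Two other sections bear on how the 2.5% should be read. Section 7.1 describes a "prospective open-label crossover randomized controlled study of the effect of CGM on hypoglycaemia compared to SMBG", so each patient serves as their own control. Section 7.6.1 defines the primary endpoint as a contrast between the two monitoring methods: "Difference (monitoring with CGM vs. SMBG) in time spent with glucose value <3.0 mmol/L (level 2 hypoglycaemia"). For the analysis, section 8.3.1 says: "CGM metrics collected in periods with monitoring using CGM vs. SMBG are compared using multiple linear regression models".

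**The concern.** In its usual sense, the standard error of an estimate shrinks as the sample grows. It is therefore a result of choosing a sample size, not the input from which one is derived. Read that way, the figure also contradicts the sentence it stands in, because an effect of 1.5 points with a standard error of 2.5 points is far from detectable.

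This is the only variability figure behind the power claim for the primary endpoint of the randomised sub study. If it had been misused in the calculation, and not merely misnamed, 24 patients could be too few. A related worry is that 2.5% might be the spread between patients within one period. The power would then depend on a within-patient correlation that the protocol does not give.

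**Working it through.** **Inputs (protocol section 7.8).** Effect δ = 0.5 × 3 = 1.5 percentage points; two-sided α = 0.05; power at least 80%; n = 24; variability figure 2.5 percentage points. The paired structure comes from sections 7.1 and 7.6.1.

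**1. Reproducing the stated figure.** Take 2.5 as the standard deviation (SD) of the within-patient difference and use a two-sided paired t-test.

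- Standard error at n = 24: 2.5/√24 = 0.510.
- Noncentrality: 1.5/0.510 = 2.94, with 23 degrees of freedom.
- Power from the noncentral t distribution: 80.4% at n = 24 and 78.5% at n = 23.
- With one degree of freedom given up for a period term (my assumption about the regression model), power at n = 24 is 80.2%.

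The smallest n that reaches 80% is therefore 24, as the protocol states. The normal approximation, ((1.960 + 0.842) × 2.5/1.5)² = 21.8, would give 22, so the stated figure matches the t-based calculation.

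**2. The literal readings.**

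- Standard error of the estimated difference = 2.5: effect over standard error is 1.5/2.5 = 0.6. Power is Φ(0.6 − 1.960) + Φ(−0.6 − 1.960) = 0.092, about 9%.
- Standard error needed for 80% power (normal approximation): 1.5/(1.960 + 0.842) = 0.535.
- Standard error of a mean of 24 = 2.5: the SD would be 2.5 × √24 = 12.2, and the normal approximation would require about 523 patients.

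Neither gives 24 patients at 80%, so neither can be what was used.

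**3. The per-period reading.** If 2.5 is the SD within each period and ρ is the within-patient correlation, the SD of the difference is 2.5 × √(2(1 − ρ)). The values of ρ below are assumptions; the protocol gives none.

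| ρ | SD of difference | Power at n = 24 |
|---|---|---|
| 0 | 3.54 | 51% |
| 0.3 | 2.96 | 66% |
| 0.4 | 2.74 | 73% |
| 0.5 | 2.50 | 80% |
| 0.7 | 1.94 | 95% |

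This reading reproduces 24 patients only with ρ at or very near 0.5, where it coincides with step 1. At any higher correlation the power exceeds 80%.

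**4. Other designs.** Two parallel groups with SD 2.5 would need 44 per arm by the normal approximation. A one-sided paired calculation on the same approximation gives 17.2, hence 18. Neither matches.

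**The case for a change.** The best case for a correction is that the sentence is wrong as it stands, that it carries the power claim for the primary endpoint, and that arithmetic cannot show where the 2.5 came from. A per-period SD of 2.5 with a correlation of 0.5 gives the same answer as an SD of the difference of 2.5. The figure was borrowed from another population, and only the sponsor's own calculation can settle which quantity it was. Rewording one sentence would cost little.

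The first part stands: the term is wrong or at best unqualified, and its origin cannot be confirmed from the protocol. Two things limit it.

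- The term is not impossible as an input. The residual standard error of a regression is a residual SD and does not shrink with n. In a model of the paired differences with only an intercept, it is the SD of the difference. Section 8.3.1 plans linear regression, although section 7.8 does not use the word residual.
- The harmful version needs two facts that the protocol does not state: that 2.5% is a per-period SD, and that the correlation is below 0.5. A sponsor who began from a per-period SD must still have assumed a correlation of about 0.5 to arrive at 24. The figures of 51% to 73% are therefore hypothetical and do not estimate this trial's power.

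**Conclusion.** No change to the plan follows. The wording is a clerical slip: 2.5 percentage points cannot be the standard error of the estimated difference, since that gives about 9% power against the 80% claimed. The design, the endpoint, the effect, the error rate and the sample size together let a statistician recover the likely meaning. With 2.5 as the SD of the within-patient difference, 24 patients give 80.4% power and 23 give 78.5%. Correcting the term would leave the sample size, the stated power, the endpoint and the analysis as they are.

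This rests on two inferences: that 2.5% is the SD of the difference, and that sizing used a paired t-test. Section 7.8 states neither, but together they reproduce the plan's figure exactly. The conclusion is limited to the label. It does not show that an SD of 2.5 points, taken from older adults with type 1 diabetes, will prove right in patients with post-pancreatitis diabetes; the protocol itself says that adequate data were not available.

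### Sub study 1: enrolling 30 patients does not preserve the required 24 at the stated 25% dropout; it covers 20%

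*Protocol*

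**What the plan says.** Protocol section 7.8 (Sample size considerations) gives the calculation for sub study 1 on the primary endpoint, the percentage of time with glucose below 3.0 mmol/L. The base size is stated as "A sample size of 24 patients is determined to have at least 80% power to detect a reduction". The inputs are a halving of that time from a starting level of 3%, a two-sided alpha of 5%, and a variability figure given, in percentage points, as "standard error of 2.5". The allowance for loss follows directly: "To account for approximately 25% dropouts, the final sample size is set to 30 patients".

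The protocol does not show how 24 became 30, and it does not name the test behind the 24. Section 7.1 describes the design as a "prospective open-label crossover randomized controlled study of the effect of CGM on hypoglycaemia compared to SMBG in PPDM patients". Section 7.6.1 defines the primary endpoint as the CGM versus SMBG difference over the final two weeks of each period.

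**The concern.** An allowance for dropout should leave the required number of patients after the expected loss. The enrolment figure is therefore the required number divided by the fraction retained. Here 30 equals 24 multiplied by 1.25, which is not the same as 24 divided by 0.75 and always gives too small a number.

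Completers are the relevant unit. The endpoint is a within-patient contrast, and a patient who leaves before the end of the second period supplies no such contrast. If the base size of 24 has no reserve, the power claimed for the primary endpoint is not met at the dropout rate the protocol itself expects. A reader weighing a null result would then credit the trial with more power than it was designed to have.

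**Working it through.** **Inputs (Protocol 7.8 unless noted)**

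- Difference to detect: 50% of 3% = 1.5 percentage points.
- Variability: 2.5 percentage points. The text calls this a standard error. I read it as the SD of the within-patient difference; this is an assumption, made because it reproduces the stated 24.
- Two-sided alpha 0.05; target power at least 80%.
- Crossover design, each patient serving as own control (7.1).
- Dropout about 25%; final size 30.

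**Step 1: reproduce the 24.** Two-sided paired t-test with noncentrality λ = (1.5 / 2.5) × √n = 0.6√n and n − 1 degrees of freedom. Power = P(|T| > t₀.₉₇₅,ₙ₋₁), where T is noncentral t with parameter λ.

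| Completers | λ = 0.6√n | Power, n − 1 df | Power, n − 2 df (two-sequence crossover) |
|---|---|---|---|
| 22 | 2.81 | 76.5% | 76.3% |
| 23 | 2.88 | 78.5% | 78.3% |
| 24 | 2.94 | 80.4% | 80.2% |
| 32 | 3.39 | 90.8% | 90.7% |

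The smallest n with at least 80% power is 24, so the protocol's figure is reproduced exactly and carries no reserve.

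Other readings do not give 24:

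- The normal approximation gives ((1.960 + 0.842) × 2.5 / 1.5)² = 21.8, that is 22.
- Two parallel arms would need 44 per arm.

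**Step 2: check the allowance.**

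- Stated route, inferred from the exact match: 24 × 1.25 = 30.
- Required at 25% loss: 24 / (1 − 0.25) = 32.
- Left from 30 at 25% loss: 30 × 0.75 = 22.5.
- Largest loss that 30 can absorb: 1 − 24/30 = 20%.

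In whole patients, 6 losses (20%) leave 24, 7 losses (23.3%) leave 23 and 8 losses (26.7%) leave 22.

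**Step 3: power at the stated dropout.** With 30 enrolled and 25% lost, power is 78.5% (23 completers) or 76.5% (22). Interpolating the formula at 22.5 gives 77.5%. The shortfall from 80% is 80 − 78.5 = 1.5 to 80 − 76.5 = 3.5 points.

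As a further check, suppose each patient independently drops out with probability 25% (my assumption). Then 30 enrolled yield at least 24 completers with probability 35%, and average power is 77.1%.

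**The case against.** Several points can be made for the protocol.

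- **The dropout rate is only approximate.** True, but 30 works only at 20% or less. With 7 or 8 losses, the whole-patient counts on either side of 25%, fewer than 24 remain. If 20% is what is meant, the text should say so.
- **The power statement is attached to 24 patients and is correct for 24.** This stands. What fails is the implied claim that enrolling 30 secures those 24 at the stated loss.
- **The multiplication by 1.25 is inferred.** Also correct. The contradiction does not depend on how 30 was reached.
- **Reading 2.5% as the SD of differences is an assumption.** This stands and limits the power figures. If 2.5% is the SD of a single measurement, power at 24 depends on a within-patient correlation that the protocol does not give: 51% at 0, 63% at 0.25, 80% at 0.5 and 98% at 0.75. That is a larger uncertainty than the one discussed here. The completer count of 22.5 does not depend on it.
- **Under a normal approximation, 22 completers still give 80.4%.** True, but that method would have produced 22 as the required number, not 24.
- **Other sections might close the gap.** Section 8.3.2 ends the sub studies once observations matching the planned sizes are collected, which could be read as continued recruitment; the planned size may equally mean 30 enrolled. Section 7.4 covers withdrawal without mentioning replacement. Section 8.3.3 leaves missing data to the analysis plan, and a model using single-period patients might recover a little information. The sample size statement relies on none of these.

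The strongest point is size: one or two patients and a few points of power, on inputs that section 7.8 says were borrowed from older adults with type 1 diabetes.

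**Conclusion.** The concern holds. At the protocol's own 25% dropout, 30 patients give 22 to 23 completers instead of 24. On the calculation that reproduces the 24, power is then 76.5% to 78.5%, which is 1.5 to 3.5 points under the stated minimum of 80%.

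The completer arithmetic rests only on figures in section 7.8 and on dropouts not being replaced. The power figures also rest on a paired t-test and on 2.5% being the SD of within-patient differences. The effect is modest and leaves design, conduct and analysis untouched, but the statement is wrong as written and should be corrected.

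**What to change.** Amend the sentence in section 7.8 in one of two ways, with enrolment kept at 30:

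1. State that 30 patients allow for 20% dropout, leaving 24 completers and 80% power.
2. Keep 25% dropout and state that 30 patients are expected to give 22 to 23 completers, with power of about 77% (76.5% at 22, 78.5% at 23).

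The choice should follow the dropout rate the investigators actually expect. The same edit should say what the 2.5% denotes, because the power figures depend on it.

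The cost is a wording change, with no extra patients or procedures; under the second option the reported power is slightly less favourable. If both 25% dropout and 80% power are to be kept, enrolment would have to be 32, which is two more patients.

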7.3 Eligibility criteria

7.3.1 Inclusion criteria PPDM patients

- Signed informed consent before any study specific procedures*
- Able to read and understand Danish
- Male or female age $\geq 18 \leq 80$ years
- A definitive diagnosis of chronic pancreatitis based on the M-ANNHEIM criteria²⁰
- A diagnosis of insulin treated PPDM based on the World Health Organization criteria for diabetes (HbA1c $\geq 6.5\%$ (48 mmol/mol) and/or fasting plasma glucose ≥ 126 mg/dl (7.0 mmol/l) > 3 months after diagnosis of pancreatitis

*a signed informed consent is waived for patients in sub study 2 which is a register-based study based on data from Diabetesdatabasen in the North Denmark Region.

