7.3.2 Exclusion criteria PPDM patients

- Known or suspected abdominal cancer (incl. intestine, pancreas, and the hepato-biliary system)
- Severe pre-existing comorbidities (assessed by investigator upon inclusion)
- Attack of acute or chronic pancreatitis requiring admission within four weeks prior to inclusion
- Use of glucocorticoid medications within four weeks prior to inclusion
- Presence of autoimmune antibodies suggestive of type 1 diabetes
- Prior pancreatic surgery (including total pancreatectomy, pancreaticoduodenectomy, distal pancreatectomy, pancreaticojejunostomy, enucleation, or Frey procedure)
- Prior gastric surgery or vagotomy
- Autoimmune pancreatitis

7.3.3 Comparator groups for sub studies 1 and 3 (individuals with type 2 diabetes)

- Individuals with type 2 diabetes enrolled in the DiaMonT study are included as comparator group in sub studies 1 and 3. Individuals participating in the DiaMonT study undergo CGM for up to three months and provide information on experience with hypoglycaemia and awareness. These data will be used for comparison with the data collected in sub studies 1 and 3. The DiaMonT study is already approved by relevant regulatory bodies (N-20200068) and participants have provided written informed consent upon inclusion and agreed that the collected data can be used for research purposes.
- Individuals with type 2 diabetes are matched to PPDM patients based on HbA1c levels and other relevant parameters including regimens of glucose lowering therapy.
- The following data from the DiaMonT study will be used:
 - Basic demographic and clinical characteristics
 - Information on glucose lowering therapies and other medications
 - Routine biochemical parameters including Hb1Ac
 - CGM metrics
 - Information on hypoglycaemia and hypoglycaemia awareness

Patients from the DiaMonT study will not provide any biological material for this project. Data will be used in compliance with the rules on protection of personal data from the Danish Data Protection Agency.

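### Is sub study 2's expectation of at least 75 PPDM cases unsound because it makes no allowance for the eligibility criteria?

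*Protocol*

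**What the plan says.** Protocol section 7.8 explains that sub study 2 uses data already collected, so its size is set by what the register holds. It then gives an expectation in three steps. From earlier work by the same group, "the proportion of patients with PPDM among patients clinically diagnosed type 1 or type 2 diabetes is approximately 1.5" per cent. For the register, "In Diabetesdatabasen there are currently >5000 unique adult individuals registered". The conclusion is "thus we expect to identify at least 75 PPDM cases which should provide sufficient statistical power to the planned analyses", with a previous study by the group cited in support. No effect size, standard deviation, numerical power or matching ratio is given for this sub study.

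Section 7.3.1 sets the case criteria. They include "A definitive diagnosis of chronic pancreatitis based on the M-ANNHEIM criteria" and "A diagnosis of insulin treated PPDM based on the World Health Organization criteria for diabetes", with an age range of 18 to 80 years. Its footnote mentions sub study 2 by name, but only to say that "a signed informed consent is waived for patients in sub study 2". Section 7.3.2 lists the exclusions, among them "Prior pancreatic surgery (including total pancreatectomy, pancreaticoduodenectomy, distal pancreatectomy, pancreaticojejunostomy, enucleation, or Frey procedure") and "Severe pre-existing comorbidities (assessed by investigator upon inclusion"). Section 7.3.4 gives sub study 2 its own comparator group; no separate case criteria are given for it.

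**The concern.** The 1.5% is described as the share of all people with a clinical diagnosis of type 1 or type 2 diabetes who have PPDM. The cases that section 7.3 admits are a subset of these: insulin treated, with definite chronic pancreatitis, no older than 80 and without previous pancreatic surgery. Because the footnote lifts only the consent requirement for sub study 2, the natural reading is that the other criteria stand. Yet section 7.8 goes straight from register size to case count, calls the result a minimum, and rests its statement about power on it in the same sentence.

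If the eligible number were well below 75, the primary comparison of HbA1c variability independent of the mean would be less precise than a reader of section 7.8 would suppose. A reader also cannot tell whether the 75 is meant before or after the criteria are applied.

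**Working it through.** **Inputs.** Register size N: more than 5000 adults (section 7.8). PPDM proportion: about 1.5% (section 7.8). Eligible share f, meaning the fraction of PPDM cases that meet sections 7.3.1 and 7.3.2: not given in the protocol, so any value below is an assumption.

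**The plan's figure.** 5000 × 0.015 = 75.0. The stated number is reproduced exactly, and no step lies between the register floor and the 75.

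**Is 75 a minimum before any exclusion?** Not strictly. If each of exactly 5000 people had a 1.5% chance of being a case, the count would be Binomial(5000, 0.015). The chance of 75 or more is then 0.52, and the central 95% range is 59 to 92. Rounding matters a little too: at 1.45% the product is 5000 × 0.0145 = 72.5. Pulling the other way, the register is larger than 5000 by an amount the protocol does not state.

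**Effect of the criteria.** Expected eligible cases = N × 0.015 × f. At the floor of exactly 5000:

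| Assumed f | Eligible cases (75 × f) | Register needed for 75 eligible (5000 / f) |
|---|---|---|
| 0.9 | 67.5 | 5556 |
| 0.8 | 60 | 6250 |
| 0.5 | 37.5 | 10,000 |

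Read the other way, 75 eligible cases require N × f = 5000. The break-even share is therefore 100% at N = 5000, 5000/6000 = 83% at 6000, 5000/7500 = 67% at 7500, and 50% at 10,000.

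**What this shows.** Whether 75 eligible cases are available depends on two quantities, N and f. The protocol bounds N from below only and does not give f. Nothing in it favours one row of the table over another, and the middle column describes a register of exactly 5000, whereas the protocol says it is larger.

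**Which criteria could bite.** The lower age limit removes nobody, since section 7.8 already counts adults. The chronic pancreatitis criterion may overlap largely with PPDM as the protocol uses the term, because section 6.1 introduces it as a complication of that disease. Insulin treatment and prior pancreatic surgery are the clearest restrictions for which no allowance is stated.

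**The case for a change.** The strongest case for a change is that the protocol itself makes the claim. It states a number, calls it a minimum, and says in the same breath that power is sufficient. Power depends on the cases that enter the comparison, so replying that the sentence speaks only of identifying cases does not fully answer the point. The criteria in section 7.3 can only leave the count unchanged or reduce it, and the remedy would be cheap: one register count and a sentence. A case definition settled before extraction would also prevent it from being chosen once the count is known.

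Much of this stands as a comment on wording. The phrase promises more than the multiplication supports, and the reference to power cannot be reproduced from what is given. It does not establish an error, however. The sentence gives an expectation for a study whose size the register fixes, not a recruitment target or a numerical power that the design then fails to deliver. Whether the 1.5% already reflects some of the criteria depends on cited studies that are not at hand.

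Some exclusions, such as the comorbidity judgement made by an investigator at inclusion, fit poorly with a sub study that has no visits. How such items are applied to a register extract is ordinarily settled in the statistical analysis plan, which was not available here. That gap is not evidence against the figure of 75.

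**Conclusion.** The observation is accurate but calls for no change. The 75 is the unreduced product of the register floor and 1.5%, and the protocol does not say whether it is before or after the section 7.3 criteria. It is best read as an expected count of identified PPDM cases.

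No shortfall is shown. Its existence and size rest on the true register size and the eligible share, neither of which the protocol gives, so the counts of 67.5, 60 and 37.5 are illustrations at assumed shares of 90%, 80% and 50% and a register of exactly 5000.

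Nothing in conduct or inference turns on the sentence. Recruitment plays no part, the available cases come from the register whatever section 7.8 predicts, and the comparison of HbA1c variability would be the same. The number of cases found and the confidence interval for the difference will show the precision achieved. Saying which side of the criteria the 75 falls on would be a courtesy to the reader. It is a missing detail that analysts will fill when they extract the data.
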